#### **f. HOW SUPPLIED**

1. Exemestane is available in 25 mg tablets.
2. Exemestane is commercially available and will not be supplied.

### **6.1.2 Letrozole**

#### **a. PHARMACOLOGY**

Mechanism of Action: Letrozole binds to the heme group of aromatase, which catalyzes the conversion of androgens to estrogens. Inhibition of aromatase significantly decreases plasma estrogen levels.

#### **b. PHARMACOKINETICS**

1. **Absorption:** Letrozole is rapidly and well absorbed. Absorption is not affected by food.
2. **Distribution:** The volume of distribution of letrozole is approximately 1.9 L/kg. It is weakly protein bound.
3. **Metabolism:** Letrozole is metabolized in the liver via CYP3A4 and CYP2A6 to an inactive carbinol metabolite. Letrozole is also a strong inhibitor of CYP2A6 in vitro.
4. **Elimination:** Letrozole is primarily excreted in the urine, predominantly as a glucuronide carbinol metabolite. The elimination half-life is approximately 2 days.

#### **c. ADVERSE EFFECTS**

##### **1. Adverse Events with Possible Relationship to Letrozole**

###### **Likely (>20%)**

- Hotflashes

###### **Less likely (< 20%)**

- Edema
- Hypertension
- Cataracts
- Abdominal pain
- Constipation
- Diarrhea
- Dyspepsia
- Nausea
- Vomiting
- Nightsweats
- Pain
- Hypercalcemia
- Weight gain or loss
- Hypercholesterolemia
- Arthralgia
- Arthritis
- Back pain
- Bone pain
- Limb pain
- Myalgia
- Osteoporosis
- Weakness
- Dizziness
- Fatigue
- Headache
- Somnolence
- Anxiety
- Depression
- Urinary tract infection
- Vaginal bleeding
- Vaginal irritation
- Cough
- Alopecia
- Pruritis
- Rash

Rare but serious (<3%)

- Chest pain
- Cerebrovascular event
- Thromboembolic event
- Infection
- Viral infection
- Influenza

- Fracture
- Dyspnea
- Pleural effusion

\*< 1%, postmarketing, and case reports: anaphylactic reaction, angioedema, appetite increased, arterial thrombosis, blurred vision, cardiac failure, carpal tunnel syndrome, dry skin, dysesthesia, endometrial cancer, endometrial hyperplasia, endometrial proliferation, erythema multiforme, eye irritation, fever, hepatitis, hypoesthesia, irritability, leukopenia, liver enzymes increased, memory impairment, nervousness, palpitations, paresthesia, stomatitis, tachycardia, taste disturbance, thirst, thrombocytopenia, toxic epidermal necrolysis, trigger finger, urinary frequency increased, urticaria, vaginal discharge, xerostomia

2. Pregnancy and Lactation: Pregnancy category X. It is not known if letrozole is excreted in human milk.

3. Drug Interactions: Letrozole is a strong CYP2A6 inhibitor and moderate CYP2C19 inhibitor. Due to potential drug interactions, a complete patient medication list, including letrozole, should be screened prior to initiation of letrozole. Refer to the current FDA-approved package insert for additional information.

4. Hepatic Impairment: Letrozole is metabolized in the liver and dose adjustment is recommended in hepatic impairment.

#### **d. DOSING & ADMINISTRATION**

Letrozole is administered in 2.5 mg tablets orally once daily with or without food.

#### **e. STORAGE & STABILITY**

Refer to the current FDA-approved package insert for storage, stability and special handling information.

#### **f. HOW SUPPLIED**

Letrozole is commercially available in 2.5 mg tablets, and will not be supplied.

## **7.0 DOSE MODIFICATION**

NCI Common Terminology Criteria for Adverse Events. This study will utilize the CTCAE (NCI Common Terminology Criteria for Adverse Events) Version 4.0 for toxicity and Serious Adverse Event reporting. A copy of the CTCAE Version 4.0 can be downloaded from the CTEP home page (<http://ctep.cancer.gov>). The dose modifications are for events that are possibly, probably or definitely related to the study drug.

Missed doses are to be omitted rather than made up. If multiple toxicities are experienced, dose modifications will be based on the toxicity requiring the largest dose reduction. Reductions are based on the dose given in the preceding reporting period and

are based on toxicities observed since the prior toxicity evaluation. Once dose is reduced, patients will continue at new dose. No dose reescalations are allowed. There are no dose modifications for endocrine therapy.

## 7.1 Dose modifications and delays for aromatase inhibitors

There is no dose modification for anastrazole, letrozole or exemestane. Aromatase inhibitor therapy may be held for grade 3 or greater arthralgia or myalgia, and switching to another aromatase inhibitor will be allowed if symptoms resolve to grade 2 or less. If the aromatase inhibitor is held for greater than 4 consecutive weeks due to toxicity, then study treatment will be discontinued.

## 7.2 Dose modifications and delays for everolimus

For patients who do not tolerate the protocol-specified dosing schedule, dose adjustments are permitted in order to allow the patient to continue the study treatment. Details of study treatment schedule adjustments and dose levels are provided in [Table 2](#).

### Special Populations

Geriatrics ( $\geq 65$  years) :

No dosage adjustment is required.

Renal impairment :

No dosage adjustment is required.

Ethnicity :

Pharmacokinetic characteristics are similar for Caucasian and Japanese subjects.

Pharmacokinetic studies in Black transplant patients have shown an average 20% higher clearance.

**Table 2** Study treatment schedule adjustments and dose levels

Dose level	Dose and schedule
0 (starting dose)	10 mg/day
-1	5 mg/day
-2	2.5 mg/day

- If a patient is already at dose level -2 and again meets criteria for dose reduction, everolimus will be discontinued and the patient will continue on study treatment with the aromatase inhibitor therapy only.

Table 3 and Table 4 list the dosing guidelines for Everolimus-related non-hematologic and hematologic toxicities.

**Table 3** Dosing guidelines for Everolimus-related non-hematologic toxicities

Toxicity	Action
Non-Infectious Pneumonitis	Please refer to Table 0.
Reactivation of HBV or HCV flare	
Patients with a known diagnosis of hepatitis B or C infection will be excluded from study participation. Patient who meet criteria for hepatitis B or C screening and are found to have positive serology indicating an ongoing infection, will be excluded from study participation. For all other patient who start study treatment and are subsequently found to have a hepatitis B reactivation or hepatitis C flare, please refer to tables 6 and 7.
 
Table

AST or ALT elevation Grade 1 ( $>$ ULN - 3.0 x ULN) Grade 2 ( $>$ 3.0 - 5.0 x ULN)	Maintain current dose level
AST or ALT elevation Grade 3 ( $>$ 5.0 - 20.0 ULN)*	
Interrupt Everolimus administration until resolution to <math>\leq</math> grade 1 (or <math>\leq</math> grade 2 if baseline values were within the range of grade 2). If resolution occurs <math>\leq</math> 7 days, Everolimus should be re-started at the dose level prior to interruption.
 
If resolution takes <math>></math> 7 days, or if event recurs within 28 days, hold Everolimus until recovery to <math>\leq</math> grade 1 or baseline grade / value and reintroduce Everolimus at one dose level lower, if available.

AST or ALT elevation Grade 4 ( $>$ 20 x ULN)*	
Interrupt Everolimus administration until resolution to <math>\leq</math> grade 1 (or <math>\leq</math> grade 2 if baseline values were within the range of grade 2). If resolution occurs <math>\leq</math> 7 days, Everolimus should be re-started at one dose level lower. If resolution takes <math>></math> 7 days, discontinue Everolimus.

Recurrence of grade 4 after dose reduction or toxicity requiring Everolimus interruption for $>$ 28 days	Discontinue Everolimus.
Intolerable grade 2 mucositis, or grade 3 AE, except hyperglycemia or hypertriglyceridemia or hypercholesterolemia (see Section 7.3.6 )	
Interrupt Everolimus administration until resolution to <math>\leq</math> grade 1 or baseline grade / value.
 
If resolution occurs within <math>\leq</math> 7 days, Everolimus should be re-started at the dose level prior to interruption.
 
If resolution takes <math>></math> 7 days, or if event recurs within 28 days, hold Everolimus until recovery to <math>\leq</math> grade 1 or baseline grade / value and reintroduce Everolimus at one dose level lower, if available.
 
Patients will be withdrawn from the study if they fail to recover to <math>\leq</math> grade 1 or baseline grade / value within 28 days.

Any other grade 4	Hold Everolimus until recovery to grade $\leq$ 1 or baseline value Reintroduce Everolimus at one dose level lower, if available.
Grade 3 or 4 clinical liver failure (asterixis or encephalopathy/coma)	Discontinue Everolimus
Recurrence of intolerable grade 2 mucositis or grade 3 event after dose reduction	Reduce dose to the next lower dose level, if available. The lowest possible dose level of Everolimus is 2.5 mg daily. Below this level, Everolimus must be discontinued.
Recurrence of grade 4 after dose reduction	Discontinue Everolimus

Toxicity	Action
Any non-hematologic toxicity requiring Everolimus interruption for > 28 days	Discontinue Everolimus

\* Should HCV flare be confirmed, the guidelines for flare must take precedence (Table )

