### 7.3.5 Management of stomatitis / oral mucositis / mouth ulcers

Adverse Drug Reaction/severity	Afinitor Dose Adjustment and Management Recommendations	
Grade 1 Stomatitis Minimal symptoms, normal diet	No dose adjustment required. Manage with non-alcoholic or salt water (0.9%) mouth wash severaltimes a day.	
Grade 2 stomatitis Symptomatic but can eat and swallow modified diet	Temporary dose interruption until recovery to grade $\leq 1$ . Re-initiate Afinitor at same dose. If stomatitis recurs at grade 2, interrupt dose until recovery to grade $\leq 1$ . Re-initiate Afinitor at lower dose. Manage with topical analgesic mouth treatments (e.g. benzocaine, butyl aminobenzoate, tetracaine hydrochloride, methol or phenol) with or without topical corticosteroids (i.e. triamcinolone oral paste)*.	
Grade 3 stomatitis Symptomatic and unable to adequately eat or hydrate orally	Temporary dose interruption until recovery to grade $\leq 1$ . Re-initiate Afinitor at lower dose. Manage with topical analgesic mouth treatments (i.e. benzocaine, butyl aminobenzoate, tetracaine hydrochloride, methol or phenol) with or without topical corticosteroids (i.e. triamcinolone oral paste)*	
Grade 4 stomatitis Symptoms associated with life-threatening consequences	Grade 4 Discontinue Afinitor and treat with appropriate medical therapy.	

\* using agents containing hydrogen peroxide, iodine, and thyme derivatives in management of stomatitis as they may worsen mouth ulcers.

Patients with a clinical history of stomatitis/mucositis/mouth ulcers and those with gastrointestinal morbidity associated with mouth/dental infections, irritation of esophageal mucosa e.g. gastroesophageal reflux disease (GERD) and pre-existing stomatitis/mucositis must be monitored even more closely. Patients should be instructed to report the first onset of buccal mucosa irritation/reddening to their study physician immediately.

Stomatitis/oral mucositis/mouth ulcers due to Everolimus should be treated using local supportive care. Please note that investigators in earlier trials have described the oral toxicities associated with Everolimus as mouth ulcers, rather than mucositis or stomatitis. If your examination reveals mouth ulcers rather than a more general inflammation of the mouth, please classify the adverse event as such. The suggested paradigm for treatment of stomatitis/oral mucositis/mouth ulcers is as follows:

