### **7.3.6 Management of nausea**

Routine premedication for nausea is not necessary, but symptomatic patients should be treated with standard antinausea/antiemetic therapy as necessary. If the patient vomits after taking the tablets, the dose should not be replaced. Patients should resume the next regularly scheduled dose.

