### **7.3.8 Management of hyperlipidemia and hyperglycemia**

Dyslipidemia (including hypercholesterolemia and hypertriglyceridemia) has been reported in patients taking everolimus. Monitoring of blood cholesterol and triglycerides prior to the start of everolimus therapy and periodically thereafter as well as management with appropriate medical therapy is recommended.

Adverse Drug Reaction	Severity	Afinitor Dose Adjustment and Management Recommendations
Metabolic events (e.g. hyperglycemia, dyslipidemia)	Grade 1	No dose adjustment required. Initiate appropriate medical therapy and monitor.
	Grade 2	No dose adjustment required. Manage with appropriate medical therapy and monitor.
	Grade 3	Temporary dose interruption. Re-initiate Afinitor at lower dose. Manage with appropriate medical therapy and monitor.
	Grade 4	Discontinue Afinitor and treat with appropriate medical therapy.

Treatment of hyperlipidemia should take into account the pre-treatment status and dietary habits of the patient. Blood tests to monitor hyperlipidemia must be taken in the fasting state. Grade 2 or higher hypercholesterolemia ( $>300$  mg/dL or  $7.75$  mmol/L) or grade 2 hypertriglyceridemia or higher ( $> 300$  mg/dL -  $500$  mg/dL;  $>3.42$  mmol/L-  $5.7$  mmol/L) should be treated with a 3-hydroxy-3-methyl-glutaryl (HMG)-CoA reductase inhibitor (e.g. atorvastatin, pravastatin, fluvastatin) or appropriate triglyceride-lowering medication, in addition to diet.

Note: Concomitant therapy with fibrates and an HMG-CoA reductase inhibitor is associated with an increased risk of a rare but serious skeletal muscle toxicity manifested by rhabdomyolysis, markedly elevated creatine phosphokinase (CPK) levels and myoglobinuria, acute renal failure and sometimes death. The risk versus benefit of using this therapy should be determined for individual patients based on their risk of cardiovascular complications of hyperlipidemia.

Hyperglycemia has been reported inpatients taking everolimus. The fasting state of patients should be verified when interpreting results. Monitoring of fasting serum glucose is recommended prior to the start of everolimus and periodically thereafter. Optimal glycemic control should be achieved before starting a patient on Everolimus. More frequent monitoring is recommended when everolimus is co-administered with other drugs that may induce hyperglycemia.

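### Table 3, read literally, restarts everolimus after a first grade 4 metabolic event or grade 4 stomatitis, while Sections 7.3.8 and 7.3.5 say to stop it

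*Combined protocol and SAP*

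**What the plan says.** **Section 7.2, Table 3.** The table has separate rows for pneumonitis, hepatitis reactivation or flare, AST/ALT elevation, clinical liver failure and recurrent grade 4 toxicity. Remaining grade 4 events fall in a catch-all row: hold everolimus until grade 1 or below "or baseline value Reintroduce Everolimus at one dose level lower, if available".

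The row for intolerable grade 2 mucositis and grade 3 events carries an exemption: "except hyperglycemia or hypertriglyceridemia or hypercholesterolemia (see" Section 7.3.6). The grade 4 row does not repeat it.

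**Section 7.3.6.** The pointer lands on nausea management: "Routine premedication for nausea is not necessary, but symptomatic patients should be treated with standard antinausea/antiemetic therapy as necessary".

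**Section 7.3.8.** This is where hyperglycemia and dyslipidemia are covered. The grade 4 instruction is "Discontinue Afinitor and treat with appropriate medical therapy".

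**Section 7.3.5.** The grade 4 stomatitis instruction is "Grade 4 Discontinue Afinitor and treat with appropriate medical therapy".

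**Precedence.** Table 3 sends the reader elsewhere for pneumonitis and for hepatitis, and its one footnote on precedence concerns HCV flare. Section 7.0 says the largest reduction governs when a patient has several toxicities. Neither provision addresses two instructions for one metabolic or stomatitis event.

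**The concern.** Two parts of one protocol give different everolimus instructions for the same grade 4 event, and nothing says which governs. A site working from Table 3 alone would re-expose a patient after an event for which another section requires stopping. A site working from Section 7.3 would not.

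Two features make the Table 3 reading easy to reach. The metabolic exemption is written into the grade 3 row and left out of the grade 4 row, which suggests that grade 4 metabolic events are meant to be included. A reader who follows the pointer arrives at nausea and never meets the instruction to discontinue.

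What is at stake is patient safety and uniform dosing between the two institutions. Tolerability is a secondary objective, so dose-modification data handled under two rules would also be harder to interpret.

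**Working it through.** No figure in the plan needs reproducing. The check sets the rules side by side.

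**Inputs.** Table 2 gives dose levels of 10, 5 and 2.5 mg/day. A patient at 2.5 mg/day who again meets the criteria for reduction stops everolimus and continues the aromatase inhibitor alone. Table 3 also stops everolimus when grade 4 recurs after a dose reduction and when an interruption exceeds 28 days.

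**Step 1: first grade 4 metabolic event or grade 4 stomatitis, recovered within 28 days.**

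| Dose at event (mg/day) | Table 3 catch-all row | 7.3.8 or 7.3.5 | Difference (mg/day) |
|---|---|---|---|
| 10 | 5 | 0 | 5 − 0 = 5 |
| 5 | 2.5 | 0 | 2.5 − 0 = 2.5 |
| 2.5 | stop | stop | none |

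The 5 mg/day line assumes that the earlier reduction was not for a grade 4 event; otherwise the recurrence rule may already require stopping. If recovery takes more than 28 days, both texts stop everolimus.

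**Step 2: does the literal result fit the rest of the scheme?** Section 7.3.8 already requires interruption and a lower restart dose for a grade 3 metabolic event. Under the Table 3 catch-all row, a grade 4 metabolic event has the same consequence as a grade 3 one. That suggests an omission in the table rather than a deliberate rule.

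**Step 3: the pointer.** The exemption cites 7.3.6, which is nausea. The metabolic rules are in 7.3.8. The reference is wrong.

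**Step 4: lower grades of stomatitis.** Table 3 and 7.3.5 also differ in two narrower situations.

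- *Grade 3, resolved within 7 days, no recurrence within 28 days.* Table 3: "Everolimus should be re-started at the dose level prior to interruption". Section 7.3.5: "Re-initiate Afinitor at lower dose. Manage with topical analgesic mouth treatments (i.e. benzocaine" and similar agents). From 10 mg/day this is 10 versus 5. If resolution takes longer than 7 days, "or if event recurs within 28 days, hold Everolimus until recovery to" grade 1 or baseline, Table 3 also restarts one level down, so both texts give 5.
- *First intolerable grade 2 mucositis lasting more than 7 days.* Table 3 restarts one level down; 7.3.5 restarts at the same dose and reduces only on recurrence. From 10 mg/day this is 5 versus 10.

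At grade 3, Section 7.3.5 is the stricter text. At grade 2, Table 3 is.

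**The case against.** The strongest reply is that specific guidance displaces general guidance. Section 7.3 is headed as covering specific toxicities, its tables have explicit grade 4 rows, and the Table 3 row is expressly for other events. On that reading the answer is discontinuation, and many clinicians would take the stricter course anyway. Section 7.2 speaks of adjustments as permitted, which hardly obliges anyone to re-challenge. The reading is natural, but the protocol does not state it. Table 3 refers the reader elsewhere for pneumonitis and hepatitis, does not do so for stomatitis, and names mucositis in two of its own rows.

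The safeguards are also real: restart requires recovery, and long interruption or grade 4 recurrence after reduction ends everolimus. They limit the exposure without removing the contradiction. The wrong pointer is clerical, as is other misnumbering in Section 7.3, but here it hides the governing instruction.

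Three stronger readings are tempting and unsupported.

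- *A frequency.* Section 6.1.1 lists stomatitis and hyperglycemia among grade 3/4 reactions with incidence from 1/100 to under 1/10. A reader might turn that range into an expected number of conflicts. It pools grades 3 and 4, grade 3 metabolic events are exempt from the Table 3 row, and grade 3 stomatitis conflicts only in a narrow case. The range does not measure this problem.
- *Letting 7.3.5 prevail throughout.* A general precedence footnote looks tidy. At grade 2 it would raise the restart dose after a first event lasting more than 7 days from 5 to 10 mg/day. It would also put in doubt the Table 3 rule that withdraws a patient from the study if such an event has not recovered within 28 days.
- *A design flaw.* Nothing here touches the Simon two-stage rules or their error rates.

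**Conclusion.** The inconsistency is in the current text and should be corrected. It concerns a first grade 4 metabolic event or grade 4 stomatitis, at 10 or 5 mg/day, that recovers within 28 days. The literal table restarts at 5 or 2.5 mg/day where the specific sections give 0. The metabolic cross-reference is wrong on any reading.

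The conclusion rests on Table 3 being read as written and on the absence of a stated precedence rule for these events. It does not assume that sites would in fact re-challenge. How often the case would arise cannot be judged from the documents. The grade 2 and grade 3 stomatitis differences are genuine but run in opposite directions, so they call for a clinical choice by the sponsor rather than an editorial correction.

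**What to change.** 1. In the Table 3 catch-all grade 4 row, add: *except metabolic events (discontinue, see 7.3.8) and stomatitis/oral mucositis (discontinue, see 7.3.5)*.
2. In the grade 3 row, change the cross-reference from 7.3.6 to 7.3.8.

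Leave the grade 2 mucositis wording, the recurrence row and the 28-day withdrawal rule as they are, and add no general precedence footnote.

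Put two questions to the sponsor and ask for one rule for each: the restart dose after grade 3 stomatitis that resolves within 7 days without recurrence within 28 days (prior or lower), and the restart dose after a first intolerable grade 2 mucositis lasting more than 7 days (lower or same).

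The cost is a short written amendment to two table rows, with drug supplier review under the section on protocol amendments and IRB approval under Section 16.2. It adds no visits, tests or patients.

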**Table 4 Dosing guidelines for Everolimus-related hematologic toxicities**

Toxicity	Action
Grade 2 thrombocytopenia (platelets <75, $\geq 50 \times 10^9/L$ )	No action
Grade 3 thrombocytopenia (platelets <50, $\geq 25 \times 10^9/L$ )	Interrupt Everolimus until resolution to grade $\leq 1$ If resolution occurs $\leq 7$ days, reintroduce Everolimus at the dose level prior to interruption. If resolution occurs $> 7$ days, or event occurs within 28 days, reintroduce Everolimus at one dose level lower, if available.
Grade 4 thrombocytopenia (platelets < 25 $\times 10^9/L$ )	Interrupt Everolimus until recovery to grade $\leq 1$ . Then reintroduce Everolimus at one dose level lower, if available.
Grade 3 neutropenia or anemia (neutrophil <1, $\geq 0.5 \times 10^9/L$ )	Interrupt Everolimus until resolution to grade $\leq 1$ or baseline value If AE resolution occurs $\leq 7$ days, reintroduce Everolimus at the same dose level. If AE resolution occurs $> 7$ days, or event occurs within 28 days, reintroduce Everolimus at one dose level lower, if available.
Grade 4 neutropenia or anemia	Interrupt Everolimus until recovery to grade $\leq 1$ or baseline value. Reintroduce Everolimus at one dose level lower, if available.*
Febrile neutropenia	Interrupt Everolimus until resolution to grade $\leq 1$ (or baseline value) and no fever. Reintroduce Everolimus at one dose level lower, if available.*
Recurrence of grade 3 toxicity after dose reduction	Reduce dose to the next lower dose level, if available. The lowest possible dose level of Everolimus is 5 mg every other day (2.5 mg daily). Below this level, Everolimus must be discontinued.
*Recurrence of grade 4 toxicity (including febrile neutropenia) after dose reduction	Discontinue Everolimus
*Any hematologic toxicity requiring Everolimus interruption for > 28 days	Discontinue Everolimus

